2.3 Sample Size Justification

The enrollment planned for this study is approximately 360 patients, with up to approximately 150 patients with measurable visceral and/or nodal disease in Cohort A (ie, up to 100 patients with a deleterious BRCA1/2 mutation [with a maximum of 60 patients who have only measurable lymph node disease], and up to approximately 50 patients with a deleterious ATM mutation); up to approximately 150 patients without measurable disease in Cohort B (ie, up to approximately 100 patients with a deleterious BRCA1/2 mutation and 50 patients with a deleterious ATM mutation); and up to approximately 60 patients with or without measurable visceral and/or nodal disease who have a deleterious mutation in a HRR gene other than BRCA1/2 or ATM in Cohort C.

Cohort A

Cohort A will be divided into 2 sub-cohorts defined by deleterious gene mutation (BRCA1/2 vs. ATM).

Cohort A (BRCA1/2)

A Simon 2-stage design to evaluate confirmed ORR by modified RECIST Version 1.1 criteria per investigator will be used. With rolling enrollment, after the first 37 patients with a

deleterious BRCA1/2 mutation have either: a) completed 16 weeks of treatment or b) discontinued treatment prior to completing, an analysis will be performed (ie, Stage 1). If $\leq 8/37$ patients in Stage 1 have a confirmed objective response (CR or PR per investigator and without progression in bone per PCWG3), the data monitoring committee (DMC) will evaluate the overall benefit/risk for patients with deleterious BRCA1/2 mutations in this cohort and make a recommendation whether further enrollment should be discontinued. If $\geq 9/37$ patients have a confirmed objective response, then enrollment will continue with additional patients in Stage 2. With 83 total patients with a deleterious BRCA1/2 mutation, characteristics of the Simon 2-stage design include:

- 5% probability of accepting a minimally effective drug
- 90% probability of accepting an effective drug
- ORR of 20% for a minimally effective drug
- ORR of 35% for an effective drug

If there are at least 23 responses in 83 patients with a deleterious BRCA1/2 mutation, the null hypothesis (ORR = 20%) will be rejected. This design yields a type I error rate of 5% and power of 90% when the true response rate is 35%.

Note: If the study is to proceed to Stage 2, additional patients with a deleterious BRCA1/2 mutation up to 100 total patients will be enrolled in Cohort A (BRCA1/2) if additional clinical data are requested by any Health Authority to support a regulatory filing. If sufficient evidence exists to support a regulatory filing prior to fully enrolling Cohort A (BRCA1/2), enrollment may be discontinued early.

Cohort A (ATM)

Patients in Cohort A (ATM), having a deleterious ATM mutation, will be enrolled concurrently with patients from Cohort A (BRCA1/2). It is expected that about 1/3 of the Cohort A patients will have a deleterious ATM mutation. If 100 patients are enrolled in Cohort A (BRCA1/2), then approximately 50 patients would be expected to enroll into Cohort A (ATM).

A Simon 2-stage design to evaluate confirmed ORR by modified RECIST Version 1.1 criteria per investigator will be used. Characteristics of the Simon 2-stage (minimax) design include:

- 5% probability of accepting a minimally effective drug
- 80% probability of accepting an effective drug
- ORR of 20% for a minimally effective drug
- ORR of 35% for an effective drug

In the first stage, 31 patients with a deleterious ATM mutation will be evaluated. If there are 6 or fewer responses, the DMC will consider stopping the sub-cohort for futility. If the sub-cohort proceeds to the second stage ($\geq 7/31$ responders), additional patients will be accrued for a total of approximately 50. According to the Simon 2-stage parameters, if there are at

least 16 responses in a total of 53 patients, the null hypothesis (ORR = 20%) would be rejected.

Cohort B

Cohort B will be divided into 2 sub-cohorts defined by deleterious gene mutation (BRCA1/2 vs. ATM). Cohort B will be enrolled concurrently with Cohort A and is expected to enroll at approximately the same rate as Cohort A. Enrollment in Cohort B (both sub-cohorts) will be halted when Cohort A (BRCA1/2) is fully enrolled.

Cohort B (BRCA1/2)

A Simon 2-stage type futility rule will be employed in Cohort B (BRCA1/2). The Stage 1 analysis will be performed after the first 19 patients have either: a) completed 16 weeks of treatment; or b) discontinued treatment prior to completing. Enrollment into the study will continue while this analysis occurs. If $\leq 4/19$ patients in Stage 1 have a PSA response ($\geq 50\%$ decrease from baseline), the DMC will evaluate the overall benefit/risk for patients with a deleterious BRCA1/2 mutation in this sub-cohort and make a recommendation whether further enrollment should be discontinued. If $\geq 5/19$ patients have a PSA response, then enrollment will continue in Stage 2. With 54 total patients with a deleterious BRCA1/2 mutation, characteristics of the Simon 2-stage design include:

- 5% probability of accepting a minimally effective drug
- 90% probability of accepting an effective drug
- ORR of 20% for a minimally effective drug
- ORR of 40% for an effective drug

If there are at least 16 responses in 54 patients with a deleterious BRCA1/2 mutation, the null hypothesis (ORR = 20%) will be rejected. This design yields a type I error rate of 5% and power of 90% when the true response rate is 40%. Additionally, if the criteria for Stage 2 are met, additional patients, up to approximately 100 total, may be enrolled. Enrollment in Cohort B (BRCA1/2) will be halted when Cohort A (BRCA1/2) is fully enrolled.

Cohort B (ATM)

Patients in Cohort B (ATM), having a deleterious ATM mutation, will be enrolled concurrently with patients from Cohort B (BRCA1/2). It is expected that about 1/3 of the Cohort B patients will have a deleterious ATM mutation. If 100 patients are enrolled in Cohort B (BRCA1/2), then approximately 50 patients would be expected to enroll in Cohort B (ATM).

A Simon 2-stage type futility rule will be employed. The Stage 1 analysis will be performed after the first 18 patients have either: a) completed 16 weeks of treatment; or b) discontinued treatment prior to completing. Enrollment into the study will continue while this analysis occurs. If $\leq 4/18$ patients in Stage 1 have a PSA response ($\geq 50\%$ decrease from baseline), the DMC will evaluate the overall benefit/risk for patients with a deleterious ATM mutation in this cohort and make a recommendation whether further enrollment should be

discontinued. If $\geq 5/18$ patients have a PSA response, then enrollment will continue in Stage 2. With 33 total patients with a deleterious ATM mutation, characteristics of the Simon 2-stage (minimax) design include:

- 5% probability of accepting a minimally effective drug
- 80% probability of accepting an effective drug
- ORR of 20% for a minimally effective drug
- ORR of 40% for an effective drug

If there are at least 11 responses in 33 patients with a deleterious ATM mutation, the null hypothesis (ORR = 20%) will be rejected. This design yields a type I error rate of 5% and power of 80% when the true response rate is 40%. Additionally, if the criteria for Stage 2 are met, additional patients, up to approximately 50 total, may be enrolled. Enrollment in Cohort B (ATM) will be halted when Cohort A (BRCA1/2) is fully enrolled.

Cohort C

Up to approximately 60 patients will be enrolled in Cohort C. Enrollment in Cohort C will be halted when Cohort A (BRCA1/2) is fully enrolled. Since this cohort will enroll patients that have a deleterious mutation in 1 of several different deleterious HRR genes, each gene will be examined separately. It is anticipated that < 6 patients will have a deleterious mutation in the same HRR gene; however, if enrollment of patients with a deleterious mutation in the same gene is higher than anticipated, then enrollment will be held at 6 patients with a deleterious mutation in the same HRR gene and a futility rule will be implemented such that if no responses are observed, then enrollment of patients with a deleterious mutation in that particular gene will be stopped, in consultation with the DMC.

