Note: If the study is to proceed to Stage 2, additional patients with a deleterious BRCA1/2 mutation up to 100 total patients (and a maximum of 60 patients with only measurable lymph node disease) will be enrolled in Cohort A (BRCA1/2) if additional clinical data is requested by the regulatory authorities to support regulatory filing. If sufficient evidence exists to support a regulatory filing prior to fully enrolling Cohort A (BRCA1/2), enrollment may be discontinued early.

Cohort A (ATM)

Patients in Cohort A (ATM), having a deleterious ATM mutation, will be enrolled concurrently with patients from Cohort A (BRCA1/2). It is expected that about 1/3 of the Cohort A patients will have deleterious ATM mutations. If 100 patients are enrolled in Cohort A (BRCA1/2), then approximately 50 patients would be expected to enroll into Cohort A (ATM).

A Simon 2-stage type futility rule will be employed in Cohort A (ATM). An interim analysis (Stage 1) will be performed after the first 31 patients have either: a) completed 16 weeks of treatment; or b) discontinued treatment prior to completing. Enrollment into the study will continue while this interim analysis occurs. If $\leq 6/31$ patients in Stage 1 have a confirmed objective response (CR or PR per investigator and without progression in bone per PCWG3), the DMC will evaluate the overall benefit/risk for patients with deleterious ATM mutations in this cohort and make a recommendation whether further enrollment should be discontinued. If $\geq 7/31$ patients have a confirmed objective response, then enrollment will continue in Stage 2. With 53 total patients with a deleterious ATM mutation, characteristics of the Simon 2-stage (minimax) design include:

- 5% probability of accepting a minimally effective drug
- 80% probability of accepting an effective drug
- ORR of 20% for a minimally effective drug
- ORR of 35% for an effective drug

If there are at least 16 responses in 53 patients with a deleterious ATM mutation, the null hypothesis (ORR = 20%) will be rejected. This design yields a type I error rate of 5% and power of 80% when the true response rate is 35%.

Cohort B

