11.4 Interim Analysis and Data Monitoring

A DMC has been incorporated into the Study conduct to provide review and assessment of the safety and efficacy data, in a systematic manner and to safeguard the interest and the safety of the participating patients in the Study. The DMC is tasked with regularly reviewing the safety and efficacy of the Study to ensure a favorable risk-benefit ratio for the patients. A separate DMC charter contains the details regarding the membership and activities of the DMC.

Simon 2-stage designs have been employed in each sub-cohort to allow futility analyses to be conducted to help assess whether each sub-cohort should proceed to full enrollment. The Sample Size Justification section ([Section 2.3](#)) contains additional detail regarding the Simon 2-stage assumptions and parameters.

Cohort A

Cohort A will be divided into 2 sub-cohorts defined by deleterious gene mutation (BRCA1/2 vs. ATM).

Cohort A (BRCA1/2)

A Simon 2-stage design to evaluate confirmed ORR by modified RECIST Version 1.1 criteria per investigator will be used. With rolling enrollment, after the first 37 patients have either: a) completed 16 weeks of treatment, or b) discontinued treatment prior to completing, an analysis will be performed (i.e., Stage 1). If $\leq 8/37$ patients in Stage 1 have a confirmed objective response (CR or PR per investigator and without progression in bone per PCWG3), the DMC will evaluate the overall risk benefit for study treatment and make a recommendation whether further enrollment should be discontinued. If $\geq 9/37$ patients have a confirmed objective response, then enrollment will continue with additional patients in Stage 2. The parameters of the Simon 2-stage design would accrue a total of 83 patients in this sub-

cohort. If there were at least 23 responses in 83 patients, the null hypothesis (ORR = 20%) would be rejected.

Note: If the study is to proceed to Stage 2, additional patients with a deleterious BRCA1/2 mutation up to 100 total patients may be enrolled in Cohort A (BRCA1/2) if additional clinical data is requested by the regulatory authorities to support regulatory filing. If sufficient evidence exists to support a regulatory filing prior to fully enrolling Cohort A (BRCA1/2), enrollment may be discontinued early.

Cohort A (ATM)

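### Cohort A's type I error, power and rejection counts belong to designs for investigator-assessed ORR, not to the primary IRR-assessed ORR, and the ATM and non-binding-look figures do not hold as stated

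*SAP*

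**What the plan says.** **Endpoint.** Confirmed ORR by central IRR, in patients whose disease IRR judges measurable at baseline, is primary for Cohort A, separately for BRCA1/2 and ATM (protocol 11.5.1; SAP Table 1, 4, 9.1 and 10.1). Investigator ORR is supportive (protocol 11.5.1; SAP 10.1). The planned analysis of IRR ORR is counts, percentages and a 95% confidence interval. No null rate, threshold or power is attached to it there, and no interval method is named.

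**Design.** For BRCA1/2, "A Simon 2-stage design to evaluate confirmed ORR by modified RECIST Version 1.1 criteria per investigator will be used" (SAP 2.3; likewise the protocol synopsis, 11.2 and 11.7, and SAP 11.4). Protocol 11.2 and SAP 2.3 describe the ATM design in the same way. Elsewhere the ATM text is a futility-type rule that names the investigator only in the Stage 1 responder definition.

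**Final rule.** For BRCA1/2, SAP 2.3 says: "If there are at least 23 responses in 83 patients with a deleterious BRCA1/2 mutation, the null hypothesis (ORR = 20%) will be rejected". For ATM, the protocol synopsis says: "If there are at least 16 responses in 53 patients with a deleterious ATM mutation, the null hypothesis (ORR = 20%) will be rejected". SAP 2.3 (ATM) and SAP 11.4 (both sub-cohorts) put the rejection in the conditional. None of these sentences names an assessor.

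**Stage 1 and sample size.** Below the Stage 1 cut-off the DMC reviews benefit and risk and will "make a recommendation whether further enrollment should be discontinued". For ATM, SAP 2.3 says that "additional patients will be accrued for a total of approximately 50", and the next sentence gives the rule for 53. BRCA1/2 may be extended to 100, and "If sufficient evidence exists to support a regulatory filing prior to fully enrolling Cohort A (BRCA1/2), enrollment may be discontinued early".

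**The concern.** The only numerical decision rule for Cohort A is attached to an open-label, supportive read. The endpoint that carries the primary conclusion has an analysis population and an interval, but nothing to pass or fail. A reader of the sample size section could take 5%, 90% and 80% as properties of the primary analysis. A report could also cite rejection of a 20% ORR from investigator reads. The data are meant to support a possible regulatory filing, so what was prespecified for IRR ORR needs to be unambiguous.

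Two further points concern whether the stated figures hold at all, whoever reads the scans. The ATM rule is written for a number of patients that the SAP does not plan to enrol. And 5% is stated for a stopping rule that the DMC may decline to follow.

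**Working it through.** **Inputs.** Null ORR 20%, alternative 35%. BRCA1/2: continue at 9/37 or more, reject at 23/83 or more. ATM: continue at 7/31 or more, reject at 16/53 or more (protocol synopsis; SAP 2.3 and 11.4). The test is one-sided by construction; the documents do not state sidedness.

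**Formula.** With X1 ~ Bin(n1, p) in Stage 1, X2 ~ Bin(n − n1, p) after it, Stage 1 minimum a and final count r:

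- look obeyed: P(reject) = Σ over x from a to n1 of P(X1 = x) · P(X2 ≥ r − x)
- look overridden: P(reject) = P(Bin(n, p) ≥ r)

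**1. The plan's own figures, look obeyed**

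| Sub-cohort | Rule | Type I error at 20% | Power at 35% | Stated |
|---|---|---|---|---|
| BRCA1/2 | 9/37, 23/83 | 0.0487 | 0.901 | 5%, 90% |
| ATM | 7/31, 16/53 | 0.0498 | 0.802 | 5%, 80% |

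Both designs reproduce.

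**2. Look overridden.** Trials that fall below the Stage 1 cut-off and still reach the final count are added back.

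- BRCA1/2: 0.0487 + 0.0081 = 0.0568 (power 0.936)
- ATM: 0.0498 + 0.0014 = 0.0512 (power 0.809)

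These are the values if enrolment always runs to the full number. With some looks followed and some not, type I error lies between the two.

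**3. ATM at the planned total of about 50, same Stage 1 rule**

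| Final count | Type I error, obeyed / overridden | Power at 35%, obeyed / overridden |
|---|---|---|
| 15/50 | 0.0592 / 0.0607 | 0.806 / 0.812 |
| 16/50 | 0.0305 / 0.0308 | 0.717 / 0.720 |

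Fifteen misses the type I error target and sixteen misses the power target. A search over all Stage 1 sizes, Stage 1 cut-offs and final counts finds no two-stage design with 45 to 52 patients that has type I error at most 5% and power at least 80%. At 53 such designs exist, including the one in the plan.

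**4. Does the planned interval imply the same rule?** The method is not named, so assume an exact (Clopper-Pearson) two-sided 95% interval.

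| Responses | Lower limit |
|---|---|
| 24/83 | 19.5% |
| 25/83 | 20.5% |
| 17/53 | 19.9% |
| 18/53 | 21.5% |

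The interval first excludes 20% at 25/83 and 18/53, not at 23 and 16. The planned interval and the stated counts are therefore different criteria.

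**5. Do the counts carry over to IRR?** Not as written. SAP 3 allows a patient to move cohort on the IRR reading of measurability, so the IRR denominator need not be 83 or 53. BRCA1/2 may also stop early or reach 100.

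**The case against.** The strongest answer is that the plan can be read coherently. SAP 11.4 says that "Simon 2-stage designs have been employed in each sub-cohort to allow futility analyses to be conducted". No efficacy section schedules a test of investigator ORR, and the SAP's conditional wording suggests that the counts only describe the design. Sizing on investigator reads and estimating by IRR with a confidence interval is a legitimate single-arm plan, and an estimation design needs no pass/fail threshold. This largely stands. It limits the point to clarification, because the indicative rejection sentences in the protocol synopsis and SAP 2.3 still read as a final efficacy decision, and nothing says which endpoint they govern.

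Second, "about 50" might turn out to be 53. Then 16/53 works, but SAP 11.4 makes ATM accrual depend on BRCA1/2 enrolment, so 53 is not assured.

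Third, the type I error excess for ATM with the look overridden is small: 5.12% against 5%. That is true; the BRCA1/2 figure is the larger one.

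Stronger readings are tempting, and the documents do not support them:

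- **That power for IRR ORR is below 90% and 80%.** It may be lower or higher. Reader agreement in mCRPC is not given. The pooled ovarian figures in protocol 3.4.2.2 (53.8% by investigator, 41.5% by independent review) show that reads can differ, but they come from another tumour type.
- **That the sponsor plans to declare success on investigator reads.** The wording leaves this open; no analysis section plans it.
- **That ATM needs 56 patients.** This holds only for a single-stage test with the look ignored (17/56). The two-stage design meets both targets at 53.

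**Conclusion.** The point holds in a limited form and should be fixed. The Cohort A rejection counts, type I error and power belong to designs declared for a supportive endpoint, and no threshold or power is tied to the primary IRR ORR. The effect of the choice of assessor cannot be sized from the documents.

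Two stated figures do not hold as written:

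- At about 50 ATM patients the choice is type I error of 5.9% to 6.1% with power of 81% (15 responses), or about 3% with power of 72% (16 responses), against a stated 5% and 80%.
- With an advisory look, type I error can reach 5.7% for BRCA1/2 and 5.1% for ATM, against a stated 5%.

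Both shortfalls come from sample size, discreteness and the non-binding look. They would be the same under either assessor. They assume exact binomial sampling, the plan's 20% and 35%, and an ATM total of exactly 50.

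**What to change.** Make these changes in the protocol synopsis, 11.2 and 11.7, and in SAP 2.3, 10.1 and 11.4:

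1. State that 23/83, 16/53, 5%, 90% and 80% are design parameters for investigator ORR, used for the futility look. Say that they are not the success rule or the power of the primary endpoint, and that a 20% ORR will not be declared rejected on investigator reads.
2. State that the primary conclusion rests on IRR ORR with a 95% confidence interval, and name the method. If it is exact, note that its lower limit first exceeds 20% at 25/83 and 18/53.
3. For ATM, reconcile 50 with 53. If about 50 stays, restate the figures: 16/50 has type I error 3.1% and power 72% at 35% (look overridden).
4. Either declare the Stage 1 look binding, or state type I error as 5.7% and 5.1% when it is overridden.

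A formal test on IRR ORR is optional. It counts as prespecified only if it is set before IRR results are reviewed. It should use the SAP 4 denominator (all treated patients measurable per IRR), reconciled with the evaluable-for-response wording in protocol 11.3 and SAP 10. Exact counts for a fixed N hold 5% only if N does not depend on observed responses, and the early-stop clause for BRCA1/2 leaves that open.

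The cost is text and a few decisions; no new data or patients. The visible price is a less favourable stated power for ATM. A binding look would also remove the DMC's discretion, so restating type I error is the lighter choice.

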11.2 Determination of Sample Size

The enrollment planned for this study is approximately 360 patients, with up to approximately 150 patients in Cohort A with measurable visceral and/or nodal disease (ie, up to 100 patients with a deleterious BRCA1/2 mutation [with a maximum of 60 patients who have only measurable lymph node disease], and up to approximately 50 patients with a deleterious ATM mutation), up to approximately 150 patients in Cohort B (ie, up to approximately 100 patients with a deleterious BRCA1/2 mutation and 50 patients with a deleterious ATM mutation), and up to approximately 60 patients in Cohort C.

Cohort A

Cohort A will be divided into 2 sub-cohorts defined by deleterious gene mutation (BRCA1/2 vs. ATM).

Cohort A (BRCA1/2)

A Simon 2-stage design to evaluate confirmed ORR by modified RECIST Version 1.1 criteria per investigator will be used. Characteristics of the Simon 2-stage design include:

- 5% probability of accepting a minimally effective drug
- 90% probability of accepting an effective drug
- ORR of 20% for a minimally effective drug
- ORR of 35% for an effective drug

In the first stage, 37 patients with a deleterious BRCA1/2 mutation will be evaluated. If the study is to proceed to the second stage, additional patients with a deleterious BRCA1/2 mutation will be accrued for a total of 83.

Note: If the study is to proceed to Stage 2, additional patients with a deleterious BRCA1/2 mutation up to 100 total patients (and a maximum of 60 patients with only measurable lymph node disease) will be enrolled in Cohort A (BRCA1/2) if additional clinical data is requested by the regulatory authorities to support regulatory filing. If sufficient evidence exists to support a regulatory filing prior to fully enrolling Cohort A (BRCA1/2), enrollment may be discontinued early.

Cohort A (ATM)

Patients in Cohort A (ATM), having a deleterious ATM mutation, will be enrolled concurrently with patients from Cohort A (BRCA1/2). It is expected that about 1/3 of the Cohort A patients will have deleterious ATM mutations. If 100 patients are enrolled in Cohort A (BRCA1/2), then approximately 50 patients would be expected to enroll into Cohort A (ATM).

A Simon 2-stage design to evaluate confirmed ORR by modified RECIST Version 1.1 criteria per investigator will be used. Characteristics of the Simon 2-stage (minimax) design include:

- 5% probability of accepting a minimally effective drug
- 80% probability of accepting an effective drug

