Patients in Cohort A (ATM), having a deleterious ATM mutation, will be enrolled concurrently with patients from Cohort A (BRCA1/2). It is expected that about 1/3 of the Cohort A patients will have deleterious ATM mutations. If 100 patients are enrolled in Cohort A (BRCA1/2), then approximately 50 patients would be expected to enroll into Cohort A (ATM).

A Simon 2-stage type futility rule will be employed in Cohort A (ATM). The Stage 1 analysis will be performed after the first 31 patients have either: a) completed 16 weeks of treatment; or b) discontinued treatment prior to completing. Enrollment into the study will continue while this analysis occurs. If $\leq 6/31$ patients in Stage 1 have a confirmed objective response (CR or PR per investigator and without progression in bone per PCWG3), the DMC will evaluate the overall benefit/risk for patients with deleterious ATM mutations in this cohort and make a recommendation whether further enrollment should be discontinued. If $\geq 7/31$ patients have a confirmed objective response, then enrollment will continue in Stage 2. If the study is to proceed to the second stage, additional patients with a deleterious ATM mutation may be accrued for a total of approximately 50, dependent upon the enrollment of Cohort A (BRCA1/2). If there are at least 16 responses in 53 patients with a deleterious ATM mutation, the null hypothesis (ORR = 20%) would be rejected.

Cohort B

Cohort B will be divided into 2 sub-cohorts defined by deleterious gene mutation (BRCA1/2 vs. ATM). Cohort B will be enrolled concurrently with Cohort A and is expected to enroll at approximately the same rate as Cohort A. Enrollment in Cohort B will be halted when Cohort A (BRCA1/2) is fully enrolled.

Cohort B (BRCA1/2)

Up to approximately 100 patients may be enrolled into Cohort B (BRCA1/2), dependent upon enrollment in Cohort A (BRCA1/2). As in Cohort A, a Simon 2-stage type futility rule will be employed. The Stage 1 analysis will be performed after the first 19 patients have either: a) completed 16 weeks of treatment; or b) discontinued treatment prior to completing. Enrollment into the study will continue while this analysis occurs. If $\leq 4/19$ patients in Stage 1 have a PSA response ($\geq 50\%$ decrease), the DMC will evaluate the overall risk benefit for study treatment. If $\geq 5/19$ patients have a PSA response, then enrollment will continue in Stage 2.

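### Cohort A (ATM): the 5%/80% design and its 16-response rule belong to 53 patients, but accrual is planned to about 50, where no cut-off meets both 5% and 80%

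*SAP*

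**What the plan says.** SAP section 2.3, Cohort A (ATM), lists the minimax characteristics (5%, 80%, ORR 20% versus 35%) and a first stage of 31 patients that continues on 7 or more responses. It then gives two different totals in adjacent sentences: Stage 2 runs until "additional patients will be accrued for a total of approximately 50", while the decision rule is "least 16 responses in a total of 53 patients, the null hypothesis (ORR = 20%) would be rejected".

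SAP section 11.4 repeats the pairing. Patients "may be accrued for a total of approximately 50, dependent upon the enrollment of Cohort A (BRCA1/2"), and then: "If there are at least 16 responses in 53 patients with a deleterious ATM mutation, the null hypothesis (ORR = 20%) would be rejected".

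The protocol is divided in the same way:

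- **53 patients.** The Synopsis, section 11.2 and section 11.7 all tie the design to 53, and section 11.2 accrues Stage 2 to 53 under the line "Characteristics of the Simon 2-stage (minimax) design include". The Synopsis also states 16 of 53 as the rule and adds "This design yields a type I error rate of 5% and power of 80% when the true response rate is 35" (per cent).
- **About 50 patients.** The enrolment limits in the Synopsis, section 6.1 and section 11.2 read, in the last of these, "up to approximately 50 patients with a deleterious ATM mutation), up to approximately 150 patients in Cohort B". SAP section 2.3 carries the same limit: "up to approximately 50 patients with a deleterious ATM mutation); up to approximately 150 patients without measurable disease in Cohort B".

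No section of either document gives a rejection count for this sub-cohort at any total other than 53. SAP section 13, which lists changes from the protocol, does not mention a move from 53 to about 50.

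**The concern.** A minimax design has the smallest maximum sample size that meets its error targets, so it has no slack below that size. Stopping at about 50 gives up part of what the design promises, and the plan does not say which part.

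The other three Simon sub-cohorts do not have this problem, because their caps exceed their Simon totals: 100 against 83 for Cohort A (BRCA1/2), 100 against 54 for Cohort B (BRCA1/2), and 50 against 33 for Cohort B (ATM). Only here is the cap below the design total.

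Two things are at stake. The stated 80% power would not be delivered at the planned accrual. The choice between 15 and 16 as the cut-off would also be left open until the response count is known, which is what a pre-specified rule should prevent.

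**Working it through.** **Inputs** (SAP 2.3 and Protocol Synopsis, Cohort A (ATM)): p0 = 0.20; p1 = 0.35; type I error 5%; power 80%; first stage n1 = 31, continue on 7 or more; final rule 16 or more of 53; planned accrual about 50.

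**Formula.** For total N and cut-off c,

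P(reject | p) = Σ over x = 7 to 31 of P(X1 = x) × P(X2 ≥ c − x),

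with X1 ~ Bin(31, p) and X2 ~ Bin(N − 31, p). Type I error is this sum at p = 0.20, and power is the sum at p = 0.35. It treats the Stage 1 stop as enforced.

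**Step 1: reproduce the plan's figure.** N = 53, c = 16 gives type I error 0.0498 and power 0.8017. The stated 5% and 80% are correct for 53.

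**Step 2: N = 50.**

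- c = 16: 0.0305 and 0.7169. The miss rate at ORR 35% is 1 − 0.7169 = 28.3%.
- c = 15: 0.0592 and 0.8057. Power is adequate, but type I error exceeds 5%.

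**Step 3: smallest cut-off with type I error at most 5%, by realised total.** The table starts at 42 because Cohort A (BRCA1/2) may end at its Simon total of 83. With ATM expected to be one third of Cohort A, that implies 83 / 2 ≈ 42 ATM patients.

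| N | Cut-off | Type I error | Power at 35% |
|---|---|---|---|
| 42 | 14 | 2.97% | 64.52% |
| 43 | 14 | 3.61% | 68.45% |
| 44 | 14 | 4.34% | 72.07% |
| 45 | 15 | 2.49% | 64.60% |
| 46 | 15 | 3.02% | 68.37% |
| 47 | 15 | 3.63% | 71.87% |
| 48 | 15 | 4.32% | 75.07% |
| 49 | 16 | 2.54% | 68.31% |
| 50 | 16 | 3.05% | 71.69% |
| 51 | 16 | 3.62% | 74.80% |
| 52 | 16 | 4.27% | 77.63% |
| 53 | 16 | 4.98% | 80.17% |

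Power is not monotone in N, because the cut-off rises in whole responses. Just above 53 the cut-off becomes 17 and power drops again: 74.6% at 54, 77.3% at 55, 79.8% at 56. The next total that meets both targets with this first stage is 57 (4.86% and 82.0%).

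**Step 4: could another first stage rescue 50?** A search over every first-stage size, first-stage boundary and final cut-off found no design meeting both 5% and 80% at any total from 10 to 52. At 50 the best valid power is 76.9% (type I error 4.88%). At 53 such designs exist, including the one in the plan.

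**Step 5: sensitivity to the non-binding stop.** The DMC only considers or recommends stopping at 6 or fewer of 31. If the look is ignored altogether, 16 of 50 gives 3.08% and 71.99%, 15 of 50 gives 6.07% and 81.22%, and 16 of 53 gives 5.12% and 80.91%. The result at 50 hardly moves.

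**The case against.** The best reply is that the word approximately lets about 50 include 53. The protocol sets a firm limit of 100 for BRCA1/2 but a soft one for ATM, and section 11.2 accrues to 53 outright. On this reading about 50 is a rounded forecast from the one-third share and 53 is the design total. As a guess at intent this is plausible. But the SAP prints the two totals in adjacent sentences as different quantities, SAP 11.4 allows accrual to fall short depending on BRCA1/2 enrolment, and even 52 fails to meet both targets.

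A second reply is that little depends on the rule. SAP 11.4 describes the Simon designs as a means of futility analysis, the SAP words this rule conditionally, and SAP section 10 reports independent-review ORR with a 95% confidence interval and no test. Keeping 16 at N = 50 is also conservative on type I error. All of this stands and limits the consequence. It does not supply the missing cut-off or make the stated 80% true at 50.

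A third reply is that 53 is special only if the Stage 1 stop is enforced. This is correct: with the look ignored, 16 of 53 slightly exceeds 5% (5.12%), and 17 of 56 meets both targets (4.32% and 80.6%). The figures for 50 are essentially unchanged.

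**Conclusion.** The point holds. The calculation behind the stated design is right for 53 patients; the fault is that the same properties and rule are attached to an accrual of about 50. There, keeping 16 gives type I error 3.0% and power 71.7%, about 8 points below the stated 80%. Lowering the cut-off to 15 restores power to 80.6% but raises type I error to 5.9%.

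These figures assume exact binomial responses, the 6/31 first stage and an enforced stop; ignoring the stop changes the N = 50 figures by less than one percentage point. The effect is limited to the Simon rejection rule on investigator-assessed ORR in this one sub-cohort. The Stage 1 look and the primary independent-review estimate with its confidence interval are unaffected. It should be corrected, but it does not threaten the primary analysis.

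**What to change.** Choose one total for Cohort A (ATM) and make every section agree.

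**Option 1: keep about 50.** State: N = 50, reject at 16 or more, type I error 3.0%, power about 72% at ORR 35%. For this sub-cohort only, this replaces:

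- the total of 53 (Protocol Synopsis, 11.2, 11.7; SAP 2.3, 11.4);
- the 5%/80% bullets and the minimax label (Protocol Synopsis, 11.2, 11.7; SAP 2.3);
- the closing type I error and power sentence (Protocol Synopsis);
- the 16-of-53 sentences (Protocol Synopsis; SAP 2.3, 11.4).

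The cost is wording only, with the stated power falling from 80% to about 72%.

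**Option 2: keep 53.** Put 53 in the enrolment limits (Protocol Synopsis, 6.1, 11.2; SAP 2.3) and in the accrual sentences (SAP 2.3, 11.4). The sentences that forecast about 50 from the one-third share can stay. Cohort A becomes 100 + 53 = 153 and the study 153 + 150 + 60 = 363, still approximately 150 and 360. The cost is wording plus about 3 more patients in the cap.

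**Under either option**, SAP 11.4 makes the final total depend on BRCA1/2 enrolment, so pre-specify the cut-off and power by realised total. The Step 3 table can be used as it stands: 14 for 42 to 44 patients, 15 for 45 to 48, and 16 for 49 to 53.
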